4. ANALYSIS SETS

The following populations are defined:

Table 1 Analysis Sets

Population	Definition
ITT Population	All patients who are randomized. Patients will be grouped according to treatment assigned at randomization.
Safety-Evaluable Population	All patients who receive any study treatment, and patients randomized to the comparator arm under observation, grouped according to treatment actually received prior to Week 52. In the PDS arm, the population includes all patients randomized to PDS receiving at least one loading dose, or any patient who received the PDS implant prior to Week 52. In the comparator arm, the population includes all patients randomized to the comparator arm who did not receive the PDS implant prior to Week 52.
PDS Safety Population	All patients who receive the PDS implant, including patients in the comparator arm who cross over to receive PDS at Week 64. Analyses on this population will only include data after first loading dose. Patients will be grouped according to treatment actually received prior to Week 52 (i.e. patients receiving PDS prior to Week 52 are grouped to the PDS arm, and patients receiving PDS after Week 52 are grouped to the comparator arm).
PDS PK Population	All patients who are randomized with at least one post implant PK sample available and who receive PDS at any time point, grouped according to treatment actually received prior to Week 52, and overall. Analysis is relative to time since implant insertion.

PDS PK Evaluable Population	All patients in the PDS PK Population excluding patients receiving intravitreal injections of ranibizumab in the study eye post PDS implant (including supplemental treatment) or patients with fellow eye ranibizumab after randomization, or bevacizumab treatment in either eye within 9 months prior to randomization or after randomization, or patients with septum dislodgment. Patients will be grouped according to treatment actually received prior to Week 52, and overall. Analysis is relative to time since implant insertion.
Aqueous Humor PK Evaluable Population	Subset of patients in the PDS PK Evaluable Population with at least one post implant aqueous humor PK sample. Patients will be grouped according to treatment actually received prior to Week 52,and overall.

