 - Non-fatal stroke AEs defined by terms from the conditions associated with central nervous system haemorrhages and cerebrovascular accidents Standardized MedDRA Query (SMQ) (Narrow), ischemic cerebrovascular conditions SMQ (Narrow), and hemorrhagic cerebrovascular conditions SMQ (Narrow) or
 - Non-fatal myocardial infarction AEs defined by terms from the myocardial infarction SMQ (Narrow) or
 - Vascular death (including deaths of unknown cause)
- Deaths
- Intraocular inflammation (according to the Standardization of Uveitis Nomenclature (SUN) classification [Jabs et al. 2005]).

AEs will be tabulated by System Organ Class (SOC) and preferred term (PT), and summarized by AE onset day (pre-implant insertion, \leq 37 days post-implant insertion, \geq 37 days post-implant insertion). Separate summaries will be prepared for ocular events in the study eye and fellow eye.

In addition, the following categories of events will be summarized for the overall PDS Safety Population by refill-exchange interval at the time of the final analysis to assess the temporal relationship of events to the refill-exchange procedure (post-operative

period (day of implant through Day 37), Day 38 through first refill-exchange, first refill-exchange through second refill-exchange, etc.):

- Ocular AEs and SAEs
- Ocular AESI and Serious Ocular AESI
- AEs leading to discontinuation of study treatment (also summarized in the Safety-Evaluable Population at Week 52) and AEs leading to explant
- Treatment or procedure related Ocular AEs and SAEs as determined by the Investigator
- AEs related to medical device deficiencies

Ocular AEs and SAEs within 9 days of intravitreal injection, implant or refill-exchange procedure will also be summarized separately. The 9-day cutoff was selected as patients return to the clinic at Day 7 (± 2 days) after implant surgery, and therefore the same window was selected for the evaluation of safety events after refill-exchanges and intravitreal injections.

Listings of AEs, SAEs, AESIs, AEs leading to early discontinuation of study treatment, AEs related to medical device deficiencies (see Section 5.4.4 of the Protocol), vitreous hemorrhage AEs, explantations, re-implantations and deaths will be provided with study day calculated both relative to randomization date and relative to the date of the PDS implant.

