5.6.2.1 Adverse Device Effects

The prospective collection of device specific ADEs or procedure specific ADEs was added to the study on 14 June 2021, 10 months after the first patient received the PDS implant in the study. No device or procedure specific ADE data prior to 14 June 2021 was collected in the EDC. Summaries of device or procedure specific ADEs include patients who received the implant after the initiation of collection of device deficiencies

on June 14, 2021. ADEs collected prior to 14 June 2021 with unspecified relation to device or procedure are reported in summaries of treatment, device, or procedure related AEs. All reported ADEs are included in the listings with suspected causality or relation to device or procedure. ADEs will be summarized in the PDS Safety Population only at the time of the primary analysis and at the final analysis.

Frequency and number of ADEs (see Section 5.4.4 of the Protocol) and serious ADEs ([SADEs] anticipated and unanticipated) will be tabulated by SOC and PT, and summarized by AE onset day (\leq 37 days post-implant insertion, > 37 days post-implant insertion) in the PDS Safety Population, through Week 52 at primary analysis and EOS at final analysis.

ADEs leading to explantation and discontinuation of study, and incidence, severity and duration of SADEs during the post-operative period will be included in listings.

ADEs as assessed by Investigator and as assessed by Sponsor will be summarized by the worst case assessment of suspectedness and seriousness.

ADEs reported to be related to the use of the investigational medical devices by users or other persons who have been exposed to the medical device but are not the study subject will be provided in a listing as these are not study subjects and do not belong to the PDS Safety Population.

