In addition to presenting the suspected/confirmed COVID-19 infections, the Sponsor developed a broad search strategy for AEs associated with COVID-19 infection to further evaluate the confirmed events of COVID-19 and reported AEs that could be considered complications of the disease. This search strategy includes both the AEs of a confirmed or suspected COVID-19 infection (PTs in Table 3) and any AEs considered associated with COVID-19 (temporally reported around PTs in Table 4). As causality to COVID-19 was not collected on the standard eCRF, the Sponsor identified associated AEs as those reported \leq 7 days before and \leq 30 days after any reported AE suggesting a confirmed COVID-19 infection (PTs listed in Table 4). The COVID-19 associated AEs for patients with confirmed COVID-19 infection will be provided in a summary table or a listing.

Table 4 Roche COVID-19 SMQ (narrow) Preferred Terms for Confirmed Cases

Coronavirus infection

Coronavirus test positive

COVID-19

COVID-19 pneumonia

SARS-CoV-2 test positive

SARS-CoV-2 sepsis

SARS-CoV-2 viraemia

COVID-19 treatment

Multisystem inflammatory syndrome in children

COVID-19 = coronavirus disease-2019; SARS-CoV-2 = severe acute respiratory coronavirus 2; SMQ = standardized MedDRA query.

5.6.3 Device Deficiencies

The prospective collection of device deficiencies was added to the study on 14th June 2021, 10 months after the first patient received the PDS implant in the study. No device deficiency data prior to 14 June 2021 was collected in the EDC.

A listing of device deficiencies including the kind of device (implant, insertion tool, initial fill needle, refill needle, explant tool), whether the deficiency could have led to an SAE or posed a serious health threat as determined by the Investigator/ Sponsor and action taken with the device will be provided.

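### The by-refill-interval row for device-deficiency AEs counts early patient-time from before device-deficiency collection began on 14 June 2021, which biases its early rates down relative to later ones

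*SAP*

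**What the plan says.** Section 5.6.2 (Adverse Events) plans a table in which five categories of "events will be summarized for the overall PDS Safety Population by refill-exchange interval at the time of the final analysis". The columns are the post-operative period (implant to Day 37), Day 38 to the first refill-exchange, first to second refill-exchange, and so on. The stated purpose is to see how events relate in time to the refill-exchange procedure. One of the five rows is "AEs related to medical device deficiencies".

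Section 4 (Table 1) defines the population without regard to implant date: "All patients who receive the PDS implant, including patients in the comparator arm who cross over to receive PDS at Week 64".

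Section 5.6.3 (Device Deficiencies) says: "No device deficiency data prior to 14 June 2021 was collected in the EDC". It places that date "10 months after the first patient received the PDS implant in the study". Section 1.1.7 confirms that collection is prospective from then.

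Section 5.6.2.1 (Adverse Device Effects) has the same start date: "No device or procedure specific ADE data prior to 14 June 2021 was collected in the EDC". For that reason it limits device- or procedure-specific ADE summaries to patients implanted after collection began. The by-interval table in Section 5.6.2 carries no such limit.

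**The concern.** An AE can be tied to a device deficiency only if deficiencies are being recorded. For PDS-arm patients implanted before 14 June 2021, some or all of the early time since implant falls in the period without recording, yet the table counts these patients in every column they pass through. The missing time is not spread evenly. It lies almost wholly in the post-operative column and the column up to the first refill, and those are the columns against which post-refill periods are compared.

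At stake is the reading of timing. A flat pattern could look like an increase after refill-exchange. A real excess around surgery could look smaller than it is, or vanish.

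**Working it through.** The SAP gives no figure for this row to reproduce, so the check is a calendar calculation.

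**Inputs from the SAP**
- Collection starts 14 June 2021, 10 months after the first implant (5.6.3). The first implant is then about 14 August 2020, 304 days earlier.
- PDS-arm implant is at about Week 4, with refills at Weeks 40, 76 and 112 (1.2), so each interval is 36 weeks = 252 days.
- Comparator implant is at Week 64 (1.2). The earliest randomisation is about 28 days before the first implant. Adding 448 days puts the earliest crossover implant at about 8 October 2021, after collection began, so crossovers are fully covered.
- About 100 patients are in the PDS arm and 60 in the comparator arm (Section 3).

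**Assumptions, not in the SAP**
- PDS-arm implants are uniform over L = 6 to 15 months from the first implant (30.4 days per month).
- 55 of 60 comparator patients are implanted.
- Every implanted patient completes the intervals shown.

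**Dates that follow**
- Implanted by about 8 May 2021 (14 June minus 37 days): the whole post-operative period precedes collection.
- Implanted by about 5 October 2020 (14 June minus 252 days): the whole time to first refill precedes collection.

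**Formula.** For an implant on day t after the first implant, and an interval from day a to day b after implant, the covered share is max(0, t + b − max(t + a, 304)) / (b − a). Average this over t uniform on 0 to L. Pooled coverage = (100 × PDS-arm share + 55 × 1) / 155.

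**Worked case, L = 10 months = 304 days**
- Post-operative (0–37): only implants on days 267–304 contribute, at an average of one half: 37 × 0.5 / 304 = 6%.
- Day 38 to first refill (37–252): zero before day 52, rising linearly to 1 at day 267, then 1: (215 × 0.5 + 37) / 304 = 144.5 / 304 = 48%.
- First to second refill (252–504): from 200/252 = 0.794 at day 0 to 1 at day 52, then 1: (52 × 0.897 + 252) / 304 = 98%.
- Pooled: (6.1 + 55)/155 = 39%; (47.5 + 55)/155 = 66%; (98.2 + 55)/155 = 99%.
- With a constant true rate, the apparent ratio of first-to-second refill to post-operative is 0.988/0.394 = 2.51. Against Day 38 to first refill it is 0.988/0.661 = 1.49.

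**Range over accrual length** (coverage shown as post-operative / Day 38 to first refill / first to second refill)

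| Accrual (months) | PDS-arm coverage | Pooled coverage | Ratio vs post-operative | Ratio vs Day 38 to first refill |
|---|---|---|---|---|
| 6 | 0 / 22 / 97% | 35 / 49 / 98% | 2.76 | 1.98 |
| 8 | 0 / 35 / 98% | 35 / 58 / 99% | 2.78 | 1.70 |
| 10 | 6 / 48 / 98% | 39 / 66 / 99% | 2.51 | 1.49 |
| 12 | 22 / 56 / 99% | 50 / 72 / 99% | 2.00 | 1.38 |
| 15 | 37 / 65 / 99% | 60 / 77 / 99% | 1.66 | 1.28 |

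From the second refill on, coverage is 100%. If the row counts only time under collection, coverage is 100% in every column and both ratios are 1.0.

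**The case against.** **The limit may already apply.** Section 5.6.2.1 sits under 5.6.2 and ties its limit to the start of device-deficiency collection. If an AE related to a device deficiency counts as a device-specific ADE, the limit could be read to cover this row. The definitions are left to the protocol, so this cannot be excluded. But on that reading the limit conflicts with the unrestricted population named for the table, and the two sections still need to be reconciled.

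**The table has other evidence on timing.** Ocular AEs, ocular AESIs and AEs leading to explant are also shown by interval, with no June 2021 start stated, and the listings give study day relative to implant. The collection date is disclosed openly. This stands and keeps the point minor.

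**Three stronger readings are tempting but not supported.**
- A reader might infer that reported rates must rise after the first refill. Only ascertainment must rise. If true events cluster around surgery, the artefact could be hidden or reversed.
- A reader might infer that the row "Treatment or procedure related Ocular AEs and SAEs as determined by the Investigator" is distorted too, because its label omits devices. The SAP does not show this. Section 5.6.2.1 says that "ADEs collected prior to 14 June 2021 with unspecified relation to device or procedure are reported in summaries of treatment, device, or procedure related" AEs, so the earlier events are kept, and the shorter label may be loose wording.
- A reader might infer a false excess in crossover patients over the PDS arm. The table is planned for the overall population, and Section 5.6.2 specifies no by-arm comparison by interval. In the pooled table the fully covered crossovers dilute the bias.

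**Conclusion.** The point holds for one of the five rows. As written, the device-deficiency row mixes early patient-time without ascertainment with later patient-time that is almost fully ascertained, so its early rates are too low relative to its later ones. The direction follows from the SAP's own dates and populations. The size does not, because accrual dates and the number of crossover implants are not given. Under the assumptions above, a constant true rate would appear about 1.7 to 2.8 times higher after the first refill than post-operatively, and about 1.3 to 2.0 times higher than from Day 38 to first refill. The second contrast is the one closest to the table's purpose, and it is the smaller. If events truly cluster around insertion, the table would understate that cluster.

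This is a minor point. The row is descriptive, it appears only at the final analysis, and no test or efficacy result depends on it.

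**What to change.** In Section 5.6.2, for the device-deficiency row only, state one of two rules:

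1. Include only patients implanted on or after 14 June 2021, in line with Section 5.6.2.1; or
2. Include only patient-intervals (or the part of an interval) on or after that date, with the number of patients or patient-time under collection as denominator.

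Under either rule, show the number under collection in each column, put any earlier events in the listing, and cross-refer to Sections 5.6.2.1 and 5.6.3 so that the population is stated once and consistently. The other four rows stay as they are.

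The cost is a sentence of SAP wording and a date filter, with no new data. The downside is fewer PDS-arm patients in the early columns. Under the accrual assumptions, 67% to 100% of PDS-arm implants came before the date, so rule 1 would keep at most about 33 of 100 PDS-arm patients and possibly none, in every column. Rule 2 loses the same early time but keeps the PDS arm almost complete from the first refill on. Its price is a rule that differs from the one in Section 5.6.2.1.

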5.6.2.1 Adverse Device Effects

The prospective collection of device specific ADEs or procedure specific ADEs was added to the study on 14 June 2021, 10 months after the first patient received the PDS implant in the study. No device or procedure specific ADE data prior to 14 June 2021 was collected in the EDC. Summaries of device or procedure specific ADEs include patients who received the implant after the initiation of collection of device deficiencies

on June 14, 2021. ADEs collected prior to 14 June 2021 with unspecified relation to device or procedure are reported in summaries of treatment, device, or procedure related AEs. All reported ADEs are included in the listings with suspected causality or relation to device or procedure. ADEs will be summarized in the PDS Safety Population only at the time of the primary analysis and at the final analysis.

Frequency and number of ADEs (see Section 5.4.4 of the Protocol) and serious ADEs ([SADEs] anticipated and unanticipated) will be tabulated by SOC and PT, and summarized by AE onset day (\leq 37 days post-implant insertion, > 37 days post-implant insertion) in the PDS Safety Population, through Week 52 at primary analysis and EOS at final analysis.

ADEs leading to explantation and discontinuation of study, and incidence, severity and duration of SADEs during the post-operative period will be included in listings.

ADEs as assessed by Investigator and as assessed by Sponsor will be summarized by the worst case assessment of suspectedness and seriousness.

ADEs reported to be related to the use of the investigational medical devices by users or other persons who have been exposed to the medical device but are not the study subject will be provided in a listing as these are not study subjects and do not belong to the PDS Safety Population.

5.6.2.2 Additional Safety Analyses Performed for COVID-19

Based on the first reports of COVID-19 infection globally, the Sponsor determined that the window for all analyses of COVID-19 associated events would start from 01 December 2019.

Following the MedDRA 23.1 release, a COVID-19 SMQ (narrow) is now available. This SMQ includes 18 terms relevant to COVID-19 infection (see Table 3), and these terms will be used to assess the impact of COVID-19. Patients with AEs from this COVID-19 SMQ (narrow) will be considered to have a confirmed or suspected COVID-19 infection.

A listing or table of confirmed and suspected COVID-19 AEs will be produced from the patients identified from the search as having confirmed or suspected COVID-19 infection (Table 3).

Table 3 Roche COVID-19 SMQ (narrow) Preferred Terms for all Cases (Confirmed and Suspected)

Asymptomatic COVID-19

Breakthrough COVID-19

Congenital COVID-19

Coronavirus infection

Coronavirus pneumonia

Coronavirus test positive

COVID-19

COVID-19 immunisation

COVID-19 pneumonia

COVID-19 prophylaxis

COVID-19 treatment

Exposure to SARS-CoV-2

Multisystem inflammatory syndrome

Multisystem inflammatory syndrome in adults

Multisystem inflammatory syndrome in children

Occupational exposure to SARS-CoV-2

Post-acute COVID-19 syndrome

SARS-CoV-2 antibody test positive

SARS-CoV-2 carrier

SARS-CoV-2 RNA decreased

SARS-CoV-2 RNA fluctuation

SARS-CoV-2 RNA increased

SARS-CoV-2 sepsis

SARS-CoV-2 test false negative

SARS-CoV-2 test positive

SARS-CoV-2 viraemia

Suspected COVID-19

Thrombosis with thrombocytopenia syndrome

Vaccine derived SARS-CoV-2 infection

COVID-19 = coronavirus disease-2019; SARS-CoV-2 = severe acute respiratory coronavirus 2; SMQ = standardized MedDRA query.

In addition to presenting the suspected/confirmed COVID-19 infections, the Sponsor developed a broad search strategy for AEs associated with COVID-19 infection to further evaluate the confirmed events of COVID-19 and reported AEs that could be considered complications of the disease. This search strategy includes both the AEs of a confirmed or suspected COVID-19 infection (PTs in Table 3) and any AEs considered associated with COVID-19 (temporally reported around PTs in Table 4). As causality to COVID-19 was not collected on the standard eCRF, the Sponsor identified associated AEs as those reported \leq 7 days before and \leq 30 days after any reported AE suggesting a confirmed COVID-19 infection (PTs listed in Table 4). The COVID-19 associated AEs for patients with confirmed COVID-19 infection will be provided in a summary table or a listing.

Table 4 Roche COVID-19 SMQ (narrow) Preferred Terms for Confirmed Cases

Coronavirus infection

Coronavirus test positive

COVID-19

COVID-19 pneumonia

SARS-CoV-2 test positive

SARS-CoV-2 sepsis

SARS-CoV-2 viraemia

COVID-19 treatment

Multisystem inflammatory syndrome in children

COVID-19 = coronavirus disease-2019; SARS-CoV-2 = severe acute respiratory coronavirus 2; SMQ = standardized MedDRA query.

5.6.3 Device Deficiencies

The prospective collection of device deficiencies was added to the study on 14th June 2021, 10 months after the first patient received the PDS implant in the study. No device deficiency data prior to 14 June 2021 was collected in the EDC.

A listing of device deficiencies including the kind of device (implant, insertion tool, initial fill needle, refill needle, explant tool), whether the deficiency could have led to an SAE or posed a serious health threat as determined by the Investigator/ Sponsor and action taken with the device will be provided.

5.6.4 Laboratory Data

HbA1c will be summarized using descriptive statistics, including change from baseline summaries and a figure of change from baseline HbA1c over time by treatment group. With the exception of HbA1_C, laboratory data will be collected at baseline only (see Protocol Section 4.5.6). These data can be used for interpretation of some AEs, no general summary is planned.

5.6.5 Vital Signs

Vital signs, height and weight measurement will be recorded at screening and final visit only. These data can be used for interpretation of some AEs, no general summary is planned.

5.6.6 Ocular Assessments

Results of the following ocular assessments will be summarized by treatment group for both the Safety-Evaluable Population and the PDS Safety Population by eye (study vs. non-study) as applicable, using descriptive summaries:

Intraocular pressure (IOP)

- Slit lamp examination
- Indirect ophthalmoscopy

Summaries of incidence of pre-dose IOP \geq 30 mmHg by treatment group will be tabulated. The presence of intraocular inflammation and vitreous hemorrhage, as determined on slit lamp examination, will be tabulated by grade (according to grading scales for flares and cells in Protocol Appendix 7, and vitreous hemorrhage density and functional scales in Protocol Appendix 8). The presence of retinal break or detachment as determined from ophthalmoscopy will be tabulated.

